5.2.3.3 GM-CSF Patient Diary/Injection Record

Patient diaries will be used to record GM-CSF SC injection compliance, site, and any injection-related symptomatic toxicity (see Appendix 11.2) during induction cycles. The Clinical Research Coordinator (CRC) at each site will collect the completed diary at start of subsequent cycle.

5.2.4 Trial Blinding/Masking

This is an open-label trial; therefore, the investigator and subject will know the treatment administered.

5.3 Randomization or Treatment Allocation

This is not a randomized trial.

5.4 Stratification

No stratification is planned.

5.5 Concomitant Medications/Vaccinations (Allowed and Prohibited)

Medications or vaccinations specifically prohibited in the exclusion criteria are not allowed during the ongoing trial. If there is a clinical indication for one of these or other medications or vaccinations specifically prohibited during the trial, discontinuation from trial therapy or vaccination may be required. The investigator should discuss any questions regarding this with the Study Chair and the Merck Clinical team. The final decision on any supportive therapy or vaccination rests with the investigator and/or the subject's primary physician.

5.5.1 Acceptable Concomitant Medications

All treatments that the investigator considers necessary for a subject's welfare may be administered at the discretion of the investigator in keeping with the community standards of medical care. All concomitant medication will be recorded on the case report form (CRF) including all prescription, over-the-counter (OTC), herbal supplements, and IV medications and fluids. If changes occur during the trial period, documentation of drug dosage, frequency, route, and date may also be included on the CRF.

All concomitant medications received within 28 days before the first dose of trial treatment and 30 days after the last dose of trial treatment should be recorded. Concomitant medications administered after 30 days after the last dose of trial treatment should be recorded for SAEs as defined in Section 7.2.

5.5.2 Prohibited Concomitant Medications

Subjects are prohibited from receiving the following therapies during the Screening and Treatment Phase (including retreatment for post-complete response relapse) of this trial:

- Antineoplastic systemic chemotherapy or biological therapy

- Immunotherapy not specified in this protocol
- Chemotherapy not specified in this protocol
- Investigational agents other than pembrolizumab and GM-CSF
- Radiation therapy
- Live vaccines within 30 days prior to the first dose of trial treatment and while participating in the trial.
 - Examples of live vaccines include, but are not limited to, the following: measles, mumps, rubella, varicella/zoster, yellow fever, rabies, BCG, and typhoid vaccine.
- Systemic glucocorticoids for any purpose other than to modulate symptoms from a suspected immune-related AE (irAE) or as premedication for iodinated contrast if not amenable to MRI imaging instead of contrast CT. The use of physiologic/replacement doses of corticosteroids may be approved after consultation with the Study Chair.
- Antiviral therapy for active HCV is not allowed during protocol therapy unless approved by the Study Chair due to unknown potential for toxicity in combination.

Subjects who, in the assessment by the investigator, require the use of any of the aforementioned treatments for clinical management should be removed from the trial. Subjects may receive other medications that the investigator deems to be medically necessary.

The Exclusion Criteria section 5.1.3 describes other medications which are prohibited in this trial.

There are no prohibited therapies during the Post-Treatment Follow-up Phase.

5.6 Rescue Medications & Supportive Care

5.6.1 Supportive Care Guidelines for Pembrolizumab

Subjects should receive appropriate supportive care measures as deemed necessary by the treating investigator. Suggested supportive care measures for the management of adverse events with potential immunologic etiology are outlined below and in greater detail in the ECI guidance document. Where appropriate, these guidelines include the use of oral or intravenous treatment with corticosteroids as well as additional anti-inflammatory agents if symptoms do not improve with administration of corticosteroids. Note that several courses of steroid tapering may be necessary as symptoms may worsen when the steroid dose is decreased. For each disorder, attempts should be made to rule out other causes such as metastatic disease or bacterial or viral infection, which might require additional supportive care. The treatment guidelines are intended to be applied when the investigator determines the events to be related to pembrolizumab.

If after the evaluation the event is determined not to be related, the investigator is instructed to follow the ECI reporting guidance but does not need to follow the treatment guidance (as outlined in the ECI guidance document). Refer to Section 5.2.2.1 for guidance on pembrolizumab dose modifications.

Suggested steroid regimens include:

- Systemic steroids equivalent to prednisone 1-2 mg/kg/day for severe immune-related toxicity requiring immunosuppressive therapy.
- Oral prednisone 0.5 mg/kg/day or other equivalent steroid regimen for mild-moderate immune-related toxicity requiring immunosuppressive therapy.
- Topical corticosteroids for mild-moderate dermatitis.
- Corticosteroid eye drops for ocular immune-related toxicity.
- Once symptoms resolve or return to Grade 1/baseline, initiate slow steroid taper over at least 4 weeks, with close monitoring.

It may be necessary to perform conditional procedures such as bronchoscopy, endoscopy, or skin photography as part of evaluation of the event. Suggested conditional procedures, as appropriate, can be found in the ECI guidance document.

- **Pneumonitis:**

- For **Grade 2 events**, treat with systemic corticosteroids. When symptoms improve to Grade 1 or less, steroid taper should be started and continued over no less than 4 weeks.
- For **Grade 3-4 events**, immediately treat with intravenous steroids. Administer additional anti-inflammatory measures, as needed.
- Add prophylactic antibiotics for opportunistic infections in the case of prolonged steroid administration.

- **Diarrhea/colitis:** Subjects should be carefully monitored for signs and symptoms of enterocolitis (such as diarrhea, abdominal pain, blood or mucus in stool, with or without fever) and of bowel perforation (such as peritoneal signs and ileus).

- All subjects who experience diarrhea/colitis should be advised to drink liberal quantities of clear fluids. If sufficient oral fluid intake is not feasible, fluid and electrolytes should be substituted via IV infusion. For Grade 2 or higher diarrhea, consider GI consultation and endoscopy to confirm or rule out colitis.
- For **Grade 2 diarrhea/colitis** that persists greater than 3 days, administer oral corticosteroids.
- For **Grade 3 or 4 diarrhea/colitis** that persists > 1 week, treat with intravenous steroids followed by high dose oral steroids.
- When symptoms improve to Grade 1 or less, steroid taper should be started and continued over no less than 4 weeks.

- **Type 1 diabetes mellitus (if new onset, including diabetic ketoacidosis [DKA]) or ≥ Grade 3 hyperglycemia, if associated with ketosis (ketonuria) or metabolic acidosis (DKA):**

- For **T1DM** or **Grade 3-4** hyperglycemia
 - Insulin replacement therapy is recommended for Type I diabetes mellitus and for Grade 3-4 hyperglycemia associated with metabolic acidosis or ketonuria.
 - Evaluate patients with serum glucose and a metabolic panel, urine ketones, glycosylated hemoglobin, and C-peptide.
- **Hypophysitis:**
 - For **Grade 2** events, treat with corticosteroids. When symptoms improve to Grade 1 or less, steroid taper should be started and continued over no less than 4 weeks. Replacement of appropriate hormones may be required as the steroid dose is tapered.
 - For **Grade 3-4** events, treat with an initial dose of IV corticosteroids followed by oral corticosteroids. When symptoms improve to Grade 1 or less, steroid taper should be started and continued over no less than 4 weeks. Replacement of appropriate hormones may be required as the steroid dose is tapered.
- **Hyperthyroidism or hypothyroidism:** Thyroid disorders can occur at any time during treatment. Monitor patients for changes in thyroid function (at the start of treatment, periodically during treatment, and as indicated based on clinical evaluation) and for clinical signs and symptoms of thyroid disorders.
 - **Grade 2** hyperthyroidism events (and **Grade 2-4** hypothyroidism):
 - In hyperthyroidism, non-selective beta-blockers (e.g. propranolol) are suggested as initial therapy.
 - In hypothyroidism, thyroid hormone replacement therapy, with levothyroxine or liothyroinine, is indicated per standard of care.
 - **Grade 3-4** hyperthyroidism events: Treat with an initial dose of IV corticosteroid followed by oral corticosteroids. When symptoms improve to Grade 1 or less, steroid taper should be started and continued over no less than 4 weeks. Replacement of appropriate hormones may be required as the steroid dose is tapered.
- **Hepatitis attributed to immune toxicity:** Assessment should be based upon greatest increase in AST, ALT, or total bilirubin. Elevations in alkaline phosphatase alone should not be used to determine treatment-related toxicity grade or supportive care interventions since this marker is commonly elevated in biliary tract cancers and may be an index of biliary obstruction independent of treatment-related toxicity. Evaluation for viral reactivation and antiviral therapy for HBV or HCV should be considered if any evidence hepatotoxicity according to standard institutional practice in HBV/HCV patients receiving anti-cancer therapies
 - For **Grade 2** events (if normal or Grade 1 at baseline), monitor liver function tests more frequently until returned to baseline values (consider weekly) to ensure not progressive.

- For **Grade 4** events and **Grade 3** if increased by greater than or equal to 50% relative to baseline and is assessed as treatment-related (e.g. no evidence of interval tumor progression or biliary obstruction), treat with intravenous corticosteroids for 24 to 48 hours.
- When symptoms improve to Grade 0-1 or baseline, a steroid taper should be started and continued over no less than 4 weeks.
- **Renal failure or Nephritis:**
 - For **Grade 2** events assessed as treatment-related and despite best supportive care (e.g. oral or IV hydration), treat with oral or systemic corticosteroids.
 - For **Grade 3-4** events, treat with systemic corticosteroids.
 - When creatinine value improves to Grade 1 or less, steroid taper should be started and continued over no less than 4 weeks.
- **Other immune-mediated adverse reactions, including ocular manifestations**
 - Permanently discontinue pembrolizumab if clinically significant or severe immune-mediated adverse reactions (see 5.2.2.1).
 - Initiate systemic corticosteroids at a dose of 1 to 2 mg/kg/day prednisone or equivalent for severe immune-mediated adverse reactions.
 - Administer corticosteroid eye drops to patients who develop uveitis, iritis, or episcleritis. Permanently discontinue ipilimumab for immune-mediated ocular disease that is unresponsive to local immunosuppressive therapy.
- **Infusion reactions:** Signs and symptoms usually develop during or shortly after drug infusion and generally resolve completely within 24 hours of completion of infusion.

Table 4 below shows treatment guidelines for subjects who experience an infusion reaction associated with administration of pembrolizumab (MK-3475).

Table 4 Infusion Reaction Treatment Guidelines

NCI CTCAE Grade	Treatment	Premedication at subsequent dosing
Grade 1 Mild reaction; infusion interruption not indicated; intervention not indicated	Increase monitoring of vital signs as medically indicated until the subject is deemed medically stable in the opinion of the investigator.	None
Grade 2 Requires infusion interruption but responds promptly to symptomatic treatment (e.g., antihistamines, NSAIDS, narcotics, IV fluids); prophylactic medications indicated for <=24 hrs	Stop Infusion and monitor symptoms. Additional appropriate medical therapy may include but is not limited to: IV fluids Antihistamines NSAIDS Acetaminophen Narcotics	Subject may be premedicated 1.5h (\pm 30 minutes) prior to infusion of pembrolizumab (MK-3475) with: Diphenhydramine 50 mg po (or equivalent dose of antihistamine). Acetaminophen 500-1000 mg po (or equivalent dose of antipyretic).

NCI CTCAE Grade	Treatment	Premedication at subsequent dosing
	
Increase monitoring of vital signs as medically indicated until the subject is deemed medically stable in the opinion of the investigator. If symptoms resolve within one hour of stopping drug infusion, the infusion may be restarted at 50% of the original infusion rate (e.g., from 100 mL/hr to 50 mL/hr). Otherwise dosing will be held until symptoms resolve and the subject should be premedicated for the next scheduled dose.
 
Subjects who develop Grade 2 toxicity despite adequate premedication should be permanently discontinued from further trial treatment administration.
	
Grades 3 or 4	
Stop Infusion.
 
Additional appropriate medical therapy may include but is not limited to:
 
IV fluids Antihistamines NSAIDS Acetaminophen Narcotics Oxygen Pressors Corticosteroids Epinephrine
 
Increase monitoring of vital signs as medically indicated until the subject is deemed medically stable in the opinion of the investigator. Hospitalization may be indicated.
 
Subject is permanently discontinued from further trial treatment administration.
	No subsequent dosing

Appropriate resuscitation equipment should be available in the room and a physician readily available during the period of drug administration.

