7.2.4 Evaluating Adverse Events

An investigator who is a qualified physician or health professional (e.g., Nurse Practitioner) will evaluate all adverse events according to the NCI Common Terminology for Adverse Events (CTCAE), version 4.0. Any adverse event which changes CTCAE grade over the course of a given episode will have each change of grade recorded on the adverse event case report forms/worksheets.

All adverse events, regardless of CTCAE grade must also be evaluated for seriousness.

Table 6 Evaluating Adverse Events

An investigator, who is a qualified physician or health care professional, will evaluate all adverse events as to:

V4.0 CTCAE Grading	Grade 1	Mild; asymptomatic or mild symptoms; clinical or diagnostic observations only; intervention not indicated.
	Grade 2	Moderate; minimal, local or noninvasive intervention indicated; limiting age-appropriate instrumental ADL.
	Grade 3	Severe or medically significant but not immediately life-threatening; hospitalization or prolongation of hospitalization indicated; disabling; limiting self-care ADL.
	Grade 4	Life-threatening consequences; urgent intervention indicated.
	Grade 5	Death related to AE
 Seriousness	A serious adverse event is any adverse event occurring at any dose or during any use of Merck product that:	
	† Results in death; or	
	† Is life-threatening; or places the subject, in the view of the investigator, at immediate risk of death from the event as it occurred (Note: This does not include an adverse event that, had it occurred in a more severe form, might have caused death.); or	
	† Results in a persistent or significant disability/incapacity (substantial disruption of one's ability to conduct normal life functions); or	
	† Results in or prolongs an existing inpatient hospitalization (hospitalization is defined as an inpatient admission, regardless of length of stay, even if the hospitalization is a precautionary measure for continued observation. (Note: Hospitalization [including hospitalization for an elective procedure] for a preexisting condition which has not worsened does not constitute a serious adverse event.); or	
	† Is a congenital anomaly/birth defect (in offspring of subject taking the product regardless of time to diagnosis); or	
	Is a new cancer; (that is not a condition of the study) or	

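### The suggested steroid timing for diarrhea/colitis in Section 5.6.1 runs backwards: Grade 3-4 waits more than a week, Grade 2 only more than 3 days.

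*Combined protocol and SAP*

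**What the plan says.** Section 5.6.1 lists suggested measures for adverse events that may be immunologic. They are meant for events the investigator judges related to pembrolizumab, and the reader is sent to the ECI guidance document for more detail.

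The diarrhea/colitis entry has two steroid lines:

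- Grade 2 "that persists greater than 3 days, administer oral corticosteroids".
- Grade 3 or 4 "that persists > 1 week, treat with intravenous steroids followed by high dose oral steroids".

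The same entry asks for monitoring for enterocolitis and bowel perforation, advises fluids for everyone affected, and asks investigators to consider GI consultation and endoscopy from Grade 2 upward. No other line in it gives Grade 3-4 an earlier steroid start.

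Table 3 (Section 5.2.2.1) holds pembrolizumab for Grade 2-3 diarrhea/colitis and stops it permanently at Grade 4. It sets no steroid start time for this toxicity.

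**The concern.** A waiting time before treatment would be expected to shorten, or at least not lengthen, as the event becomes more severe. Here it lengthens. A patient who presents at Grade 3 or 4 has no steroid instruction in the colitis entry at a time when a Grade 2 patient already has one.

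This is also hard to reconcile with Table 6 (Section 7.2.4), which describes Grade 4 as "Life-threatening consequences; urgent intervention indicated", and with Table 3, which treats Grade 4 colitis as a reason to stop pembrolizumab at once.

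What is at stake is patient safety: a clinician who applies the entry literally would start steroids later for the more dangerous event. Nothing in the statistical analysis depends on it.

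**Working it through.** No sample size, power or error rate is involved. The check compares the two thresholds with each other and then with the rest of Section 5.6.1.

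**Step 1. The two thresholds, counting the day of onset as day 1.**

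- Grade 2: more than 3 days, so the instruction first applies on day 3 + 1 = 4.
- Grade 3-4: more than 1 week, that is more than 7 days, so it first applies on day 7 + 1 = 8.
- Difference: 8 - 4 = 4 days, namely days 4, 5, 6 and 7.

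| Days since onset | Grade 2: steroid instruction in the entry | Grade 3-4: steroid instruction in the entry |
|---|---|---|
| 1-3 | none | none |
| 4-7 | oral | none |
| 8 onward | oral | intravenous, then high-dose oral |

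**Step 2. The other organ-specific Grade 3-4 steroid instructions in Section 5.6.1.**

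| Event | Instruction | Waiting time |
|---|---|---|
| Pneumonitis, Grade 3-4 | "immediately treat with intravenous steroids" | none |
| Hypophysitis, Grade 3-4 | "treat with an initial dose of IV corticosteroids followed by oral corticosteroids" | none |
| Hyperthyroidism, Grade 3-4 | "Treat with an initial dose of IV corticosteroid followed by oral corticosteroids" | none |
| Hepatitis, Grade 4 and qualifying Grade 3 | "treat with intravenous corticosteroids for 24 to 48 hours" | none |
| Renal failure or nephritis, Grade 3-4 | "events, treat with systemic corticosteroids" | none |

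So 0 of 5 have a wait. For Grade 3 hepatitis there is a qualifying condition (a rise of at least 50% over baseline, judged treatment-related), but that is not a delay. The one-week duration for AST/ALT in footnote 2 to Table 3 concerns discontinuing the patient, not starting steroids.

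**Step 3. Does anything else in the section supply an earlier start for Grade 3-4 colitis?**

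- The general list of steroid regimens at the start of Section 5.6.1 gives prednisone-equivalent 1-2 mg/kg/day for severe immune-related toxicity. It states a dose, not a start time, so it does not displace the specific colitis line.
- A similar dose appears later with an instruction to initiate, but under other immune-mediated reactions, whereas colitis has its own entry.

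**Step 4. How many patients could be affected?** This cannot be calculated. The documents give no colitis rate. The only related Grade 3 or higher rate is the interim figure in Section 8.4.4, 11% of 9 Safety Cohort patients, for all event types together.

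**The case against.** The strongest case on the other side is about consequence, since the inversion is plain on the page.

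- **The guidance is not binding.** Section 5.6.1 leaves supportive care to the treating investigator, and Section 5.5.2 permits systemic glucocorticoids for a suspected immune-related event. The general regimen for severe toxicity has no wait. This stands as a limit on harm. It does not justify a default that points the wrong way, particularly as the section intends its guidelines to be used once an event is judged related to pembrolizumab.
- **A fuller source exists.** The ECI guidance document may already give prompt Grade 3-4 timing. It is not among the documents, so this cannot be settled. If it does, the protocol contradicts its own reference. The protocol does not state what Grade 3-4 timing was intended, so complete removal of the wait is a recommendation rather than a reading of the text.
- **The path to harm is narrow.** A patient who has spent more than 3 days at Grade 2 before worsening already meets the oral-steroid line. The gap concerns patients who reach Grade 3-4 sooner. Many such events would also be serious adverse events, reported to the Study Chair within 24 business hours (Section 7.2.3.1). This stands.
- **Some pause is understandable.** Diarrhea is non-specific, and infection and other causes should be ruled out. Only the pneumonitis line says to treat immediately; the other four are silent on timing. That could explain a short delay for work-up, but not one longer than for Grade 2.
- **The reach is small.** Stages 1 and 2 are fully enrolled, so new exposure is mainly the 15 Expansion Cohort patients and anyone still on treatment. That is true, but treatment can run to 24 months or 35 cycles, with a possible Second Course.

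**Conclusion.** The concern holds. As written, the colitis entry delays the steroid instruction for Grade 3-4 by 4 days relative to Grade 2, and it is the only one of the six organ-specific Grade 3-4 steroid instructions in Section 5.6.1 with a wait. The documents offer no reason for a longer wait at higher grade.

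The conclusion rests on a literal reading of the current text and assumes that the ECI guidance document does not override it. The practical risk is reduced by investigator discretion and by the measures that do not wait, and its frequency in this trial is unknown. It should be corrected on safety grounds.

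**What to change.** Delete the one-week persistence condition from the Grade 3-4 diarrhea/colitis line in Section 5.6.1. Intravenous steroids followed by high-dose oral steroids would then apply once the event is judged related to pembrolizumab, in line with the other Grade 3-4 entries. At minimum, make the Grade 3-4 wait no longer than the 3 days used for Grade 2.

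The clinical team should confirm the final wording against the ECI guidance document so that the two agree. The cost is one phrase in a protocol amendment, with no effect on data collection, sample size or analysis.

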5.2.2.1 Dose Modifications for Pembrolizumab

Adverse events (both non-serious and serious) associated with pembrolizumab exposure may represent an immunologic etiology. These adverse events may occur shortly after the first dose or several months after the last dose of treatment. Pembrolizumab must be withheld for drug-related toxicities and severe or life-threatening AEs as per Table 3 below. As toxicity on pembrolizumab has not been shown to be dose related, dose reductions are not thought to ameliorate specific toxicities. See Section 5.6.1 and Events of Clinical Interest Guidance Document for supportive care guidelines, including use of corticosteroids.

Table 3 Dose Modification Guidelines for Pembrolizumab-Related Adverse Events

Toxicity	Hold Treatment For Grade	Timing for Restarting* Treatment	Discontinue Subject
Diarrhea/colitis	2-3	Hold until toxicity resolves to Grade 0-1	If toxicity does not resolve within 12 weeks of last dose or inability to reduce corticosteroid to 10 mg or less of prednisone or equivalent per day within 12 weeks
	4	Permanently discontinue	Permanently discontinue
AST, ALT, or increased bilirubin (despite optimal supportive care including biliary drainage if obstruction is present)	2 ^{1-3²}	Hold until toxicity resolves to Grade 0-1 or baseline grade (if Grade 2 at baseline) ¹	If toxicity does not resolve within 12 weeks of last dose
	3 ²⁻⁴	Permanently discontinue	Permanently discontinue
Type 1 diabetes mellitus (if new onset) or hyperglycemia	T1DM or 3-4	Hold for new onset Type 1 diabetes mellitus or Grade 3-4 hyperglycemia associated with evidence of beta cell failure; resume pembrolizumab when patients are clinically and metabolically stable	If toxicity does not resolve within 12 weeks of last dose or inability to reduce corticosteroid to 10 mg or less of prednisone or equivalent per day within 12 weeks
Hypophysitis	2-3	Hold until toxicity resolves to Grade 0-1	If toxicity does not resolve within 12 weeks of last dose or inability to reduce corticosteroid to 10 mg or less of prednisone or equivalent per day within 12 weeks
	4	Permanently discontinue	Permanently discontinue
Hyperthyroidism	3	Hold until toxicity resolves to Grade 0-1	If toxicity does not resolve within 12 weeks of last dose or inability to reduce corticosteroid to 10 mg or less of prednisone or equivalent per day within 12 weeks
	4	Permanently discontinue	Permanently discontinue

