Hypothyroidism	2-4	Therapy with pembrolizumab can be continued while treatment for the thyroid disorder is instituted	Therapy with pembrolizumab can be continued while treatment for the thyroid disorder is instituted
Myocarditis	Grade 1 or 2	Withhold	Based on severity of AE administer corticosteroids
	Grade 3 or 4	Permanently discontinue	
All other immune-related AEs	Intolerable/ Persistent Grade 2	Withhold	Based on type and severity of AE administer corticosteroids
Infusion reaction	3-4	Permanently discontinue	Permanently discontinue
Pneumonitis	2	Hold until toxicity resolves to Grade 0-1	If toxicity does not resolve within 12 weeks of last dose or inability to reduce corticosteroid to 10 mg or less of prednisone or equivalent per day within 12 weeks
	3-4	Permanently discontinue	Permanently discontinue
Renal failure or nephritis	2	Hold until toxicity resolves to Grade 0-1	If toxicity does not resolve within 12 weeks of last dose or inability to reduce corticosteroid to 10 mg or less of prednisone or equivalent per day within 12 weeks

Proprietary and Confidential

The information in this document is considered privileged and confidential, and may not be disclosed to others except to the extent necessary to obtain Institutional Review Board approval and informed consent, or as required by federal and state laws. Persons to whom this information is disclosed should be informed that this information is privileged and confidential and that it should not be further disclosed.

Toxicity	Hold Treatment For Grade	Timing for Restarting* Treatment	Discontinue Subject
	3-4	Permanently discontinue	Permanently discontinue
All other drug-related toxicity ³ attributed to pembrolizumab	3 or severe 2	Hold until toxicity resolves to Grade 0-1 or baseline grade if abnormal at baseline	If toxicity does not resolve within 12 weeks of last dose or inability to reduce corticosteroid to 10 mg or less of prednisone or equivalent per day within 12 weeks
	4	Permanently discontinue	Permanently discontinue

Note: Permanently discontinue for any severe AE that recurs or any life-threatening event.

* Dose interruptions or delays in start of a cycle for any reason (toxicity or non-toxicity) during Induction Phase (Cycles 1 and 2 in Efficacy Cohort (Part 2), Cycles 2 and 3 in Safety and Expansion Cohorts (Parts 1 and 3)) should be applied to both GM-CSF and pembrolizumab together so that both drugs are restarted on Day 1 of each cycle.

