¹ For patients with liver metastasis who begin treatment with Grade 2 AST or ALT, treatment is not required to be held for Grade 2 AST or ALT.

² For patients with baseline Grade 2 AST or ALT, Grade 3 AST or ALT does not automatically require treatment discontinuation. If AST or ALT increases by greater than or equal to 50% relative to baseline and is assessed as treatment-related (e.g. no evidence of interval tumor progression or biliary obstruction) and lasts for at least 1 week despite supportive care, then patients should be discontinued.

³ Patients with intolerable or persistent Grade <3 drug-related AE may hold study medication at physician discretion. Permanently discontinue study drug for persistent Grade 2 adverse reactions for which treatment with study drug has been held, that do not recover to Grade 0-1 within 12 weeks of the last dose. Patients with mild grade 3 toxicity (e.g. mild or asymptomatic rashes or asymptomatic laboratory abnormalities) may be continue on treatment with augmented supportive care and close monitoring at discretion of treating physician.

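### Section 5.6.1's ocular stopping rule names ipilimumab, which is not a study drug, and 5.6.1 and Table 3 differ on stopping pembrolizumab after a first severe, non-life-threatening immune reaction

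*Combined protocol and SAP*

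**What the plan says.** Section 5.6.1 closes its organ-by-organ guidance with a group for remaining immune-mediated reactions, expressly including ocular ones. Its first bullet reads "Permanently discontinue pembrolizumab if clinically significant or severe immune-mediated adverse reactions (see 5.2.2.1". A later bullet in the same group prescribes steroid eye drops for uveitis, iritis or episcleritis, then calls for a permanent stop of ipilimumab if immune-related eye disease does not respond to local immunosuppression.

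Section 5.2.2.1, which the first bullet cites, opens with "Pembrolizumab must be withheld for drug-related toxicities and severe or life-threatening AEs as per Table 3 below". In Table 3 the row closest to this group is labelled "All other immune-related AEs". As supplied, the only grade it lists is "Intolerable/ Persistent Grade 2", the action is to withhold, and the last column gives steroid advice without a discontinuation rule. A separate catch-all row covers other toxicity attributed to pembrolizumab. For Grade 3 or severe Grade 2 it says "Hold until toxicity resolves to Grade 0-1 or baseline grade if abnormal at baseline". It discontinues at Grade 4, or when recovery or steroid reduction is not achieved within 12 weeks.

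The table note adds "Permanently discontinue for any severe AE that recurs or any life-threatening event". Footnote 3, attached to the catch-all row, says "Patients with mild grade 3 toxicity (e.g. mild or asymptomatic rashes or asymptomatic laboratory abnormalities) may be continue on treatment with augmented supportive care". It also requires a permanent stop for a persistent Grade 2 reaction that has led to a hold and has not recovered within 12 weeks.

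Section 7.2 lists pembrolizumab and GM-CSF as the investigational products. Section 5.5.2 bars immunotherapy that the protocol does not specify.

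**The concern.** A stopping rule should tell the investigator which drug to stop and whether restarting is allowed. The ocular rule fails on the first count, because no patient in this trial receives the drug it names.

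The general bullet leaves the second question open. It orders a permanent stop and cites section 5.2.2.1 in support, but Table 3 there does not state that rule for a first severe event. An investigator whose patient recovers from a first severe Grade 3 reaction of this class can find support for a restart in the catch-all row and an order against it in 5.6.1.

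The choice matters to the patient. Under section 5.2.2 a permanent pembrolizumab stop ends protocol therapy, in a setting where section 4.1 says no treatment is established after first-line failure. In the other direction, a restart that Table 3 permits could be recorded as a departure from 5.6.1. Section 8.3.2 also counts treatment delays and tolerability discontinuations separately, so the same event could be counted as either one.

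**Working it through.** No arithmetic applies. The check sets the two sections side by side for an immune-mediated reaction outside the organ categories named in 5.6.1.

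| Event | Section 5.6.1 | Table 3, section 5.2.2.1 (as supplied) | Result |
|---|---|---|---|
| Intolerable or persistent Grade 2, judged clinically significant | Permanent stop | Immune row: withhold. Catch-all row: hold if severe Grade 2 | Differ |
| First Grade 3 event judged severe | Permanent stop | Immune row: no action shown. Catch-all row: hold, restart on recovery | Differ if the catch-all row applies; otherwise Table 3 is silent |
| Mild Grade 3 | Not clearly triggered | May continue (footnote 3, catch-all row) | No conflict shown |
| No recovery, or steroids not reducible, within 12 weeks | Permanent stop if judged significant or severe | Permanent stop (catch-all row; footnote 3 for persistent Grade 2) | No conflict |
| Grade 4 or life-threatening | Permanent stop | Permanent stop | Agree |
| Recurrent severe | Permanent stop | Permanent stop | Agree |
| Eye disease unresponsive to local treatment | Specific rule: stop ipilimumab. General bullet: stop pembrolizumab if significant or severe | No ocular row | Specific rule acts on no study drug |

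Three steps follow from the table.

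1. **Meaning of severe.** Table 6 describes CTCAE Grade 3 as severe or medically significant, but Table 3 also speaks of severe Grade 2 and mild Grade 3. The word therefore does not map strictly to Grade 3, and the difference covers events judged severe, not all Grade 3 events.

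2. **Which section governs.** Section 5.6.1 says "Refer to Section 5.2.2.1 for guidance on pembrolizumab dose modifications", which points to Table 3. It does not say that Table 3 overrides a bullet in 5.6.1 that is itself a dose instruction, and no other text sets an order of precedence.

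3. **Investigator discretion.** Section 5.2.2 lets the investigator reduce, delay or stop for any toxicity judged a risk. That permits more caution than the table. It does not authorise a restart against an instruction to stop permanently, so the open question is whether restarting is allowed.

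**The case against.** The strongest reply is that Table 3 already governs. Section 5.6.1 calls its measures suggested, to be used as the investigator sees fit. It sends dose changes to 5.2.2.1, the bullet itself cites that section, and the binding wording stands at the head of Table 3. This carries weight, and Table 3 is arguably the controlling text. But the bullet is unqualified, and nothing states that it yields.

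Second, the supplied table was read from PDF by a program. A reader might infer that the plan gives no Grade 3-4 action for other immune events. The documents do not support that: a line may have been lost, and a restored line that stops at Grade 3 would remove the main difference. A count of how many Table 3 rows state a Grade 3 action is open to the same doubt and measures no consequence. Both dose sections also point to an events-of-clinical-interest guidance document, not supplied here, which may address Grade 3 management.

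Third, the Grade 3 conflict depends on the catch-all row applying, although immune events have a row of their own. If only the immune row applies and is silent at Grade 3, the bullet fills a gap and contradicts nothing. That is fair. The Grade 2 difference arises within the immune row itself, but it requires reading an intolerable event as clinically significant, which is reasonable yet an inference.

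A reader might also conclude that Table 3 holds no permanent stop for these reactions. It does: at Grade 4, for life-threatening or recurrent severe events, and for non-recovery within 12 weeks.

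Finally, a reader might infer that refractory eye disease has no usable stopping rule. That goes too far. The general bullet names pembrolizumab and its group includes ocular events, and section 5.2.2 lets the investigator stop. Ipilimumab is evidently a slip of name. What stands is that the specific rule, which turns on failure of local treatment and needs no separate judgement of severity, names the wrong drug.

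**Conclusion.** The point holds in two limited parts. The ocular rule is wrong as written, whatever the state of the table, because it names a drug outside the trial. The general bullet and Table 3, as supplied, differ for a first, non-life-threatening event judged severe or clinically significant, and no precedence rule settles which applies.

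The second part rests on two assumptions: that the source table has no further line for other immune events that would settle the matter, and, at Grade 3, that the catch-all row reaches such events. Whether a first Grade 3 event should lead to a hold or a stop is a clinical choice that the documents do not settle.

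The number of patients affected cannot be derived, since the documents give no rate for these reactions. The consequence lies in safety management and in whether an event leads to a delay or a discontinuation. No effect on ORR, PFS6, power or sample size is claimed. The correction is worth making because these are operative safety instructions and it costs little.

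**What to change.** 1. In the ocular bullet of section 5.6.1, replace ipilimumab with pembrolizumab.
2. Replace the general bullet in that group with: *Hold or permanently discontinue pembrolizumab per Table 3 (Section 5.2.2.1), which controls dose decisions.*
3. Check the source of Table 3. If the row "All other immune-related AEs" has no Grade 3-4 line, have the safety team state the Grade 3 action there, hold or stop, with a permanent stop at Grade 4 or for recurrent Grade 3. Footnote 3's allowance for mild Grade 3 should not be extended to this row by default.

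As an editorial matter only, section 5.8 cites section 5.2.1.2 for unacceptable adverse experiences; the dose-modification text is in 5.2.2.

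The cost is one drug name, one sentence and, if needed, one table line in the next amendment, plus the cross-reference. Design, data collection and sample size are unchanged.
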